At any time during the study, based on the findings of interim data analysis, the DSMB can put the study on either temporary hold or stop the study entirely after notifying the Principal Investigator and the IRB. In the unlikely case that results show that the intervention worsens depression, the study will be stopped.

7. Risks

- a. Medical risks, listing all procedures, their major and minor risks and expected frequency.

Older individuals, especially those with chronic illness, can easily feel overwhelmed or fatigued by what would be minimally demanding tasks for others, and, therefore, we include this discomfort in the potential risks. A minority of participants may respond to certain interview questions with feelings of sadness and grief (e.g., upon being reminded of interpersonal problems and social isolation). The Principal Investigator's experience as a researcher and psychiatrist has shown that when asking delicate questions and providing feedback on sensitive topics, the vast majority of participants have sufficient coping strategies to avert the extremes of behavior that put them at risk. Additionally, peer mentors are trained to be emotionally responsive with older adult participants to alleviate distress rather than increase distress. It is expected that older adults will feel relieved to meet with peer mentors who listen actively without being directive as has been our experience in the pilot study. We expect that the proposed study will provide older adult participants with benefits such as the discussion of psychological issues with the peer mentor that may offset the inconveniences or other consequences of participation.

Expression of suicidal ideation is always a risk when working with depressed participants. We will have a protocol in place to evaluate and manage patients who express suicidal ideation. We believe the risk that patients will experience due to this intervention is very low and are further minimized by the procedures we put in place, such as initial clinical evaluation prior to being matched with a peer and regular monitoring for depressive symptoms. The peer mentor will receive supervision by a clinical social worker and consultation by a geriatric psychiatrist as needed and available at all times by telephone or pager. In the case that suicidal ideation is identified, a clinical intervention (see below).

For peer mentors who have a history of depression (an inclusion criteria for the proposed pilot RCT), the risk of worsening mental health problems is possible because the peer role requires regular interaction with depressed older adults, which can be emotionally difficult. Peer mentors may become overwhelmed in their meetings with these clients. We have designed the study to minimize the risk to peer mentors (described below).

- b. Steps taken to minimize the risks.

Undue emotional distress. Regarding undue emotional stress, peer mentors will be trained to recognize and provide support to manage undue emotional distress. Peer mentors will be trained to contact the social worker who will be available by telephone when emotional distress is extreme. A geriatric psychiatrist will be available in the case that the social worker is unable to manage the older adult's distress. Multiple strategies will be used to prevent adverse events: 1) rigorous screening of the patient's appropriateness for a peer mentoring program performed by a mental health professional prior to matching, 2) rigorous training and continuous supervision of the peer to prevent escalating emotional distress, and 3) availability of professional staff to address peer mentor's concerns by phone at all times. In the event that the peer mentor needs assistance, the peer will contact the supervising social worker who will then speak with the older adult regarding the problem. In our experience, peers were able to detect signs in the older adult of escalating distress and they were able to follow the established protocol without adverse events.

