
2. Objectives (include all primary and secondary objectives)

The specific aims of this proposal are as follows:

- (1) To measure the effect of a peer mentoring program on mild to moderate depression compared to social interaction control among minority and low-income adults aged 50+ years recruited from primary care clinics;
H1: Older adults randomized to the Peer Program (vs. control) will report decreased depression (PHQ-9 score decrease ≥ 5) at 8 weeks, 3, 6, 9 and 12 months.

We will conduct a randomized controlled trial by enrolling 160 low-income and minority adults and measure the effect of the Peer Enhanced Depression Care Program on mild to moderate depressive symptoms compared to Social Interaction Control. We will recruit a total of 10 peer mentors. The supervised peer mentors who are based in the community will provide social support by telephone with depressed older adults recruited from primary care and the

community for 8 weeks with initial training and ongoing supervision by a clinical social worker. The core components of the Peer Program are: (1) relationship building, active listening, emotionally responsive and patient-centered communication, (2) sharing of experiential knowledge by peer mentors, sharing of coping skills, modeling and communication of positive health messages regarding self-care (3) linkage to community and clinical mental health resources. In Aim 2, we will conduct a quantitative mediation analysis, specifically measuring increase in self-efficacy as the mediating factor. In Aim 3, we will use post-study key informant interviews from a diverse group of stakeholders representing individuals, the community and the primary care clinic to assess implementation process, and we will use checklists to evaluate the fidelity of the intervention.

3. Background (briefly describe pre-clinical and clinical data, current experience with procedures, drug or device, and any other relevant information to justify the research)

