We successfully contacted 85% of patients at 12 months and assessed depression with the PHQ-9 by telephone. Sixty-eight percent of patients had PHQ-9 scores that remained below baseline scores by 5 points or more. After completion of the feasibility study, we recruited 27 additional participants (total of 57 older adults) seeking to obtain greater experience with a larger sample of peers and older adults to refine the peer program. We tried telephone delivery of the program for two participants. Although peers found the telephone convenient, relationship building was more difficult, and two older adults missed telephone calls more frequently but attended in-person meetings regularly. Given the importance of problems of loneliness among our study participants, we continued with in-person meetings and used telephone calls infrequently when peers were unable to meet in person due to weather. We concluded that use of supervised peer mentors is a promising model of depression care delivery for older adults. We conducted an analysis using data from 57 older adults in the pilot study to assess whether self-efficacy predicted change in depression. We found that improvement in self-efficacy was associated with a decline in depression.

We studied peer mentor communication that would inform peer training and role development. Our aim was to describe and associate communication behaviors used by supervised peer mentors with working alliance and depression.(29) We used the Roter Interaction Analysis System, a quantitative method to analyze health communication between peers and older adults in the pilot study. We looked at a variety of communication behaviors similar to other studies on communication behaviors in mental health. (30, 31) We found that peers used a variety of skills learned in training. This included client-centered talk, positive rapport building, emotional responsiveness, and education and counseling (see Table 1). Specific communication behaviors such as emotionally responsive talk and education about psychosocial topics were associated with decreased depression (all $p < .001$). We concluded that trained peer mentors can use skilled communication behaviors that is client-centered to provide depression care services to older adults.

4. Study Procedures

- a. Study design, including the sequence and timing of study procedures (distinguish research procedures from those that are part of routine care).

Study flow

- Screen by telephone

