- If eligible, conduct clinical evaluation by telephone to assess eligibility for the study
- If not eligible, participant will be given information and a list of community and clinical resources
- If eligible, patient will undergo a baseline assessment
- Participant will be asked if willing to take part in 8 peer meetings, and 6 assessments, or Social interaction/health education visits and assessments by phone.
- If yes, we will proceed to obtain oral consent and enrollment.
- Randomization occurs
- If intervention condition -- contacted by Peer mentor -- begin 8 meetings by phone
- If control condition -- contacted by Study staff and social interaction visits
- Data collected and flagged for urgent referral if needed
- Intervention and Control conditions contacted by Study coordinator to conduct interviews by telephone, post-intervention after 8 visits and at 3 months, 6 months, 9 months and 12 months

We will collaborate with Baltimore CONNECT that was formed as a research partnership in 2013 between Johns Hopkins University and 20+ community-based social organizations. They provide a range of services from peer counseling to workforce development and nutrition support, and is now a designated non-profit. We are guided by community-engaged principles of research emphasizing a partnership approach that is equitable and includes diverse research partners.(32) The Advisory Board of Baltimore Connect will assist with recruitment of peers and help connect older adults to social services they offer. The Advisory Board will give input regarding issues of ethnicity and community culture. Preliminary findings of quantitative and qualitative analyses will be presented at quarterly meetings of the Advisory Board for feedback and interpretation, and will be integrated into the final results.

Study participants

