Randomization procedures. After a clinical and with informed consent, eligible clients will be randomized in a 1:1 ratio, to receive either: (1) the Peer Enhanced Depression Care Program or (2) Social Interaction Control. We will use MS Excel VBA-based software developed by the study statistician to allocate participants using dynamic urn minimization to balance study arms by sex.⁽³⁵⁾ These procedures will maintain allocation concealment throughout the trial, consistent with the CONSORT recommendations.⁶⁹ At the time of randomization, primary care physicians will be informed of the client's assignment with consent of the participant.

The intervention: PEERS. In our program trained and supervised older peer mentors with experiential knowledge of depression and self-care skills deliver depression care to low-income and minority older adults. The primary role of the peer mentors is to build relationship, provide emotional support, facilitate simple goal setting, share coping skills and depression self-care skills and connect to clinical and community resources for depression upon completion of the program. The program is relationship-based and takes an empowerment strategy to increase self-efficacy in depression self-care.⁽³⁶⁾ We use strategies to enhance cultural appropriateness of our program for minority and low-income older adults such as avoiding stigmatizing clinical language about mental health, respecting non-medical self-

care methods such as religious coping, taking a non-judgmental attitude, accommodating client preferences, being aware of the impact of hierarchy and power relations.(37) The peer mentor will be supervised by a licensed clinical social worker.

Matching and scheduling of visits. Once the randomization has been completed, the older adults will be informed of their assignments. The social worker will call the peer mentors to provide contact information and brief summary of the older adult with whom they are matched. Then the peer mentors will contact the older adult and set a time and place for the meeting. Peer mentors will meet with older adults for 8 meetings weekly for 45 minutes to an hour each. Each meeting will be audio-recorded. Meetings will be by telephone.

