Primary analyses will be intention-to-treat. Descriptive statistics (e.g. frequencies, means, standard deviations, medians, interquartile ranges) and graphic displays will be generated for all study variables to ensure that distributional and other assumptions of the planned analyses are met. We will minimize missing data using our team's documented retention strategies that have resulted in only 14% attrition.³⁷ All primary analyses will be adjusted for sex, demographic factors, life events, medical comorbidity, and use of mental health services. Hypothesis tests will be two-sided with $\alpha=0.05$.

c. Statistical plan including sample size justification and interim data analysis.

Table 3. Assessment schedule														
Variable	Measure	Timing of assessments												
		0 wk	1 wk	2 wk	3 wk	4 wk	5 wk	6 wk	7 wk	8 wk	3 mth	6 mth	9 mth	12 mth
Sociodemographic factors	Self-report	x												
Depression (self-report)	PHQ-9	x	x	x	x	x	x	x	x	x	x	x	x	x
Depression (assessed by clinician)	Mini-International Neuropsychiatric Interview (MINI)	x								x	x	x	x	x
Client engagement	At least 80% attendance of meetings, peer logs of meetings	x	x	x	x	x	x	x	x	x				
Client engagement	Working Alliance Inventory-SR	x	x	x	x	x	x	x	x	x				
Physical, social and emotional function	Medical Outcomes Study Short Form 36	x								x	x	x	x	x
Self-efficacy	General Self Efficacy Scale	x	x	x	x	x	x	x	x	x		x		x
Loneliness	R-UCLA Loneliness Scale	x	x	x	x	x	x	x	x	x		x		x
Coping skills	Brief Copie	x								x	x	x	x	x
Medical comorbidity	WHO WMH CIDI	x								x	x	x	x	x
Clinical and community health service use	Cornell Service Index	x								x	x	x	x	x
New uptake of counseling and antidepressant	Self-report	x	x	x	x	x	x	x	x	x				
Social determinants of Health	Accountable Health Communities Core Health-Related Social Needs Screening Questions	x								x	x	x	x	x

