8. Benefits

- a. Description of the probable benefits for the participant and for society.

The proposed study may benefit the older adult participants in terms of psychoeducation and self-care skills associated with depression, monitoring of symptoms and services delivered by a peer mentor who is under a mental health professional's supervision. The peer may benefit from increased sense of self-efficacy in helping another person and will have an increased knowledge base from the mental health training provided by the study. Benefits to society may include new knowledge regarding the provision of mental health services in the community. If the peer program is successful, new ways to provide depression care services in the community setting to low-income minority older adults will be established. The risks to the patient for participating in this project are minimal and the possibility of improving depression care is substantial.

A.4. Importance of knowledge to be gained

This research will inform the development of peer programs whose aim is to improve access and engagement of depression care among minority and low-income populations. Given that minority older adults receive inadequate or no mental health care and are less likely to access traditional mental health services, developing new methods of delivering depression care is important.

9. Payment and Remuneration

- a. Detail compensation for participants including possible total compensation, proposed bonus, and any proposed reductions or penalties for not completing the protocol.

Peer mentors - Each peer will participate in 20 hours of training conducted by the PI and also meet weekly for supervision with the social worker for each contact hour with the client. Peer mentors will be paid \$100 for attending 20 hours of training. They will be only be paid if training is completed and they are successfully matched with a

least 1 depressed older adult participant. Peer mentors will be also paid a total of \$50 for 1 meeting with a client and 1 supervision meeting. For each older adult who will receive 8 meetings with the peer, peer mentors will receive \$400. They will receive an additional \$20 for a post-study interview.

Older adult incentives - Participants will be given a token of appreciation of \$30 with for one (1) baseline assessment meeting, 8 week assessment, 3, 6, 9 and 12 month follow up assessments for total of 6 assessments for a total \$180.

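### The study flow ties the post-intervention assessment to completing 8 visits, while H1, Table 3 and the payment section place it at 8 weeks

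*Combined protocol and SAP*

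**What the plan says.** Two definitions of the same assessment appear.

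- **By visits.** The study flow in section 4.a has the coordinator interview intervention and control participants by telephone "post-intervention after 8 visits and at 3 months, 6 months, 9 months and 12 months".
- **By calendar.** H1, in section 2 and again in section 6.c, specifies "PHQ-9 score decrease ≥ 5) at 8 weeks, 3, 6, 9 and 12 months". Table 3 lists the PHQ-9 at week 0, weekly to week 8, and at the four later months. Section 9.a pays for the "8 week assessment, 3, 6, 9 and 12 month follow up assessments".

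The planned contacts are weekly in both arms. For the intervention, section 4.a states "Peer mentors will meet with older adults for 8 meetings weekly for 45 minutes to an hour each"; the comparison condition also has 8 weekly visits.

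Four other statements bear on the point. Section 4.b names the assessment that follows the 8 meetings the post-study assessment, and section 4.c says that its assessor is blinded and that no other blinding is possible. Section 7.b has peers administer the weekly PHQ-9. Section 6.c fits a mixed model to PHQ-9 by intervention week, then a durability model for months 3-12 that adjusts for the week-8 score. The analysis paragraph in section 6 states "Primary analyses will be intention-to-treat".

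**The concern.** A visit count is an outcome of treatment adherence; a calendar date is not. If the coordinator waits for the eighth visit, the assessment date moves with missed or postponed contacts, and a participant who stops early has no date at all. That sits poorly with a comparison meant to include everyone as randomized.

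This assessment also carries particular weight. It is the only one stated to be blinded. If it supplies the week-8 PHQ-9, it also gives the H1 response at 8 weeks and the adjustment variable in the durability model. No imputation method is specified for a participant who lacks that covariate.

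Incomplete attendance is foreseen. Section 6.b counts 80% attendance as engaged. Section 3 reports that 90% of pilot participants attended all 8 meetings, and that when telephone delivery was tried "two older adults missed telephone calls more frequently". Telephone is now the delivery mode.

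**Working it through.** **1. When do the two definitions coincide?** Eight weekly contacts span 7 weeks. If the first takes place *s* weeks after the time origin and *k* weeks are missed and later made up, the eighth falls at *s* + 7 + *k* weeks. This equals week 8 only when *s* + *k* = 1. For example, *s* = 1 and *k* = 0 gives week 8; *s* = 2 and *k* = 2 gives week 11. Table 3 counts from a week 0 that carries the baseline measures, but nothing ties week 0 to randomization or to the first contact. There is no window, no make-up rule, and no instruction for fewer than 8 visits.

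**2. Who might not reach the trigger?** 80% of 8 is 6.4, so a participant with 7 meetings counts as engaged yet has not reached visit 8. In the peer arm, 160/2 = 80. At the pilot rate, 10% of 80 = 8 participants would not attend all 8 meetings. That rate comes from peer meetings held mainly in person. No control-arm attendance is reported, so no count can be given for that arm.

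**3. What would such a participant lack?**

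| Item | Status |
|---|---|
| Baseline PHQ-9 and weekly scores already collected | Kept; enter the primary mixed model |
| Remaining weekly scores, peer arm | Uncertain; the peer collects them, apparently at meetings |
| Blinded post-study assessment | Could be absent |
| Week-8 PHQ-9 (H1 value, durability covariate) | Absent if that interview is its source |
| Months 3, 6, 9 and 12 | Scheduled by calendar in Table 3 |

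**4. Is power affected?** The plan states 99% for a slope difference of 0.625.

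- Effective number per arm: 160 × 0.8 / 1.2 / 2 = 53.3.
- For weeks 0-8 the sum of squares of time is 60. SE = 0.11 × √(2/(53.3 × 60)) = 0.00275.
- Power = Φ(0.625/0.00275 − 1.96), above 99.9%, in line with the stated figure.
- With a further 10% of participants lost: 160 × 0.8 × 0.9 / 1.2 / 2 = 48 per arm, still above 99%. The same holds for an error SD as large as 5.
- For a 5-point difference at one time point with an assumed SD of 7.1 (the pilot SD of change): Φ(5/(7.1 × √(2/n)) − 1.96) = 95% at n = 53.3 and 93% at n = 48.

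So the issue is bias and missing data, not sample size.

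**5. What could unequal timing do?** This is an illustration on assumptions only. Let both arms improve by *b* points per calendar week with no treatment effect. Control takes 8 weeks to reach visit 8, the peer arm takes *D* weeks, and the data are coded by visit number. The spurious difference at visit 8 is *b* × (*D* − 8).

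| *b* (points/week) | *D* = 9 | *D* = 10 | *D* = 12 |
|---|---|---|---|
| 0.3125 (half of 0.625) | 0.31 | 0.63 | 1.25 |
| 0.5 | 0.50 | 1.00 | 2.00 |
| 0.8875 (pilot 7.1/8) | 0.89 | 1.78 | 3.55 |

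Against the 5-point target this runs from 0.31/5 = 6% to 3.55/5 = 71%. Under the same assumptions, coding by time since randomization gives both arms slope *b* and no spurious difference. The plan does not say which coding intervention week means.

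**The case against.** The strongest reply is that the study-flow bullet only gives a sequence. With 8 weekly contacts, 8 visits and 8 weeks are the same planned time. H1, Table 3 and the payment section all use the calendar, and no sentence makes completion a condition of being assessed. This is fair as to intent. But the bullet is the one place that tells the coordinator when to call, and nothing states what to do when the two diverge.

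Several stronger readings are tempting, and the documents do not support them.

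- **That non-completers have no primary outcome data.** The primary model uses weekly PHQ-9 scores, and later follow-ups are on the calendar. Only the post-intervention value is exposed.
- **That timing will differ by arm because peers are volunteers and control staff are paid.** Peers are paid per meeting (sections 4.a and 9.a) and supervised weekly. Both arms share the weekly schedule and the same trigger. Arranging contacts through a peer may run at a different pace from direct calls by staff, but that is an inference.
- **That the pilot shows telephone delivery causes slippage.** The evidence is two people.
- **That the bias can be put at a given number of points.** The delays are assumed. The upper rate treats an uncontrolled pilot change as linear calendar drift. If improvement comes from the meetings, waiting longer adds little, and a delayed peer arm analyzed in actual time would show a shallower slope, the opposite direction.
- **That the plan contradicts its intention-to-treat commitment.** Analysis as randomized is still promised; the loose trigger puts complete measurement at risk.

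**Conclusion.** The concern holds in limited form. The visit-based and calendar-based definitions both stand in the plan and nothing reconciles them. Followed literally, the study flow lets post-randomization adherence decide when the only assessment stated to be blinded takes place, and some participants could lack it. Loss of the week-8 PHQ-9, and with it the H1 8-week value and the durability covariate, follows only if that interview is its source, which the plan leaves unclear.

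The size of any bias is unknown. The tabulated shifts show what unequal delay could do under stated assumptions; they are not an estimate. The change is still worth making, because it removes a dependence on adherence and needs no added participants.

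**What to change.** - Reword the study flow in section 4.a to match Table 3: assess every randomized participant in both arms at 8 weeks from randomization, for example 56 days plus or minus 7, regardless of visits completed.
- Count months 3, 6, 9 and 12 from the same origin.
- In section 6.c, define week in the primary model as time since randomization, not visit number.
- State that the blinded interview supplies the week-8 PHQ-9, if that is the intention.

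The cost is wording and coordinator scheduling. The sample size and stated power do not change. The downside is that some participants will be assessed before their last meeting, so their 8-week score will reflect an unfinished program.
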